9.4.2 Secondary Endpoints

Secondary efficacy endpoints assess the effect of IV Ampion compared to SOC on the clinical outcomes for participants with COVID-19 on supplemental oxygen. The secondary endpoints will be tested in a hierarchical manner in the order presented, and thus no adjustment to the alpha level is necessary:

Objective	Endpoint
Secondary Endpoints	
Assess the effect of Ampion compared to placebo on safety	
Incidence of adverse events (AEs) and serious adverse events (SAEs) from baseline to Day 60.
Assess the effect of Ampion compared to placebo on clinical improvement	
Change in ordinal scale from baseline through Day 7.Change in ordinal scale from baseline to hospital discharge or day 14 (whichever occurs first).Change in ordinal scale from baseline to hospital discharge or day 28 (whichever occurs first).Change in NEWS2 score from baseline through Day 5.Change in NEWS2 score from baseline to hospital discharge.Modulation of cytokine levels from baseline to Day 5.
Assess the effect of Ampion compared to placebo on duration of respiratory failure to ventilator-free days.	
Percentage of participants who progress to respiratory failure (i.e., need for mechanical ventilation, ECMO, non-invasive ventilation) by Day 28.

Objective	Endpoint
Assess the effect of Ampion compared to placebo on intensive care	
Percentage of participants who require Intensive Care Unit (ICU) admission by Day 28.ICU-free days through Day 28.ICU LOS from ICU admission to discharge.
Assess the effect of Ampion compared to placebo on hospital stay	
Hospital length of stay (LOS) from admission to discharge.Hospital-free days through Day 28.
Assess the effect of Ampion compared to placebo on oxygen use	
Duration of oxygen use, blood oxygen saturation, and oxygen flow rate from baseline through Day 5.

The efficacy endpoints will be evaluated to estimate the treatment effect and use descriptive statistics including mean, standard deviation, percentages, minimum/maximum, and 95% confidence intervals. All endpoints will be tabulated and presented by treatment arm, cohort (severe and critical), and timepoint. Where appropriate, data will be tabulated and presented cumulatively across cohorts and/or timepoints.

All binary outcomes are single incident percentages and thus the differences between the treatment groups will be tested using Fisher's exact test. The length of stay endpoints are also single incident endpoints the differences between the treatment groups will be tested using two sample t-test. All the other change from baseline variables are repeated assessments and will be analyzed utilizing a repeated measures analysis of variance.

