3.2 Secondary Endpoints

3.2.1 Change in ordinal scale from baseline through Day 7, Day 14 and Day 28.

The hypotheses to be tested are:

$$H_0: \mu_A = \mu_S \text{ versus } H_A: \mu_A \neq \mu_S$$

Where μ_A and μ_S represent the ordinal scale shift through day 7, 14, and 28 for Ampion and Placebo after randomization. The difference between Ampion and Placebo with respect to the change from baseline at day 7, 14, and 28 will be tested utilizing a Wilcoxon rank-sum test via PROC NPAR1WAY. To assess any potential time trends, an exploratory repeated measures analysis of variance will be performed with terms for treatment, time and the interaction between the two. This will be done utilizing PROC GLM with the REPEATED option.

3.2.2 Change in NEWS2 score from baseline through Day 7, or discharge if earlier.

The hypotheses to be tested are:

$$H_0: \mu_A = \mu_S \text{ versus } H_A: \mu_A \neq \mu_S$$

Where μ_A and μ_S represent the mean change from baseline in the NEWS2 score assessment through day 7 for Ampion and Placebo after randomization. The difference between Ampion and Placebo with respect to the change from baseline at day 7, or discharge if earlier, will be tested utilizing a Wilcoxon rank-sum test via PROC NPAR1WAY. To assess any potential time trends an exploratory repeated measures analysis of variance will be performed with terms for treatment, time and the interaction between the two. This will be done utilizing PROC GLM with the REPEATED option.

3.2.3 Percentage of participants who progress to respiratory failure by Day 28.

The hypotheses to be tested are:

$$H_0: \pi_A = \pi_S \text{ versus } H_A: \pi_A \neq \pi_S$$

Statistical Analysis Plan (SAP) for Clinical Study AP-017

Let π_A and π_S represent the percentage of patients who have respiratory failure for Ampion and control during the first 28 days after randomization.

This difference will be tested utilizing the appropriate chi-square test or Fisher's exact test utilizing PROC FREQ with the EXACT option, if needed.

Also, the median time to respiratory failure will be tested for difference between the two groups via the log-rank test. The log-rank test will be performed using PROC LIFETEST; and the estimation of the time-to-event distributions will be performed using the method of Kaplan and Meier.

3.2.4 Percentage of participants who require Intensive Care Unit (ICU) admission by Day 28; ICU-free days through Day 28; ICU length of stay (LOS) from ICU admission to discharge.

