8.6 Multiplicity Adjustment

The secondary analyses are considered supportive to the primary analysis. In order ensure the appropriate alpha level for all tests (without a multiplicity adjustment) a hierachial testing scheme will be employed in the order specified in Section 3.2.

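### Protocol 9.4.2 makes a significant difference in AE/SAE incidence the first step of the secondary testing order, and the SAP gives a different order without saying that it replaces the protocol's

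*Protocol*

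**What the plan says.** Protocol 9.4.2 sets the rule: "The secondary endpoints will be tested in a hierarchical manner in the order presented", and concludes from this that alpha needs no adjustment. The first row of the table that follows is "Incidence of adverse events (AEs) and serious adverse events (SAEs) from baseline to Day 60". Below the table, the protocol says of binary outcomes that "the differences between the treatment groups will be tested using Fisher's exact test". Protocol 9.2.3 sets the final alpha at 0.047.

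SAP 8.6 also specifies a hierarchy, but a different one: "a hierachial testing scheme will be employed in the order specified in Section 3.2". That section opens with "Change in ordinal scale from baseline through Day 7, Day 14 and Day 28" and has no adverse event entry. AE/SAE incidence is tested in SAP 8.4.1, among the safety analyses and outside that order. SAP 6.1 sets the final alpha at about 0.049.

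SAP Section 9, which lists changes from the protocol, says only that the secondary endpoints are now in a hierarchical order. It does not say that this order differs from the protocol's or which one governs.

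**The concern.** In a fixed sequence each step is tested at full alpha because testing ends at the first non-significant result. If the first step asks whether adverse event rates differ, a drug with the same rates as placebo is expected to fail it. The ordinal scale, NEWS2, respiratory failure, ICU and length-of-stay endpoints could then not be formally tested, however large the benefit. Because the test is two-sided, an excess of adverse events on Ampion would also satisfy the first step and open the efficacy tests.

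The second problem is that there are two prespecified orders. Which secondary results may be claimed depends on which document is followed, and neither settles that. A choice made after unblinding could be shaped by the results.

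**Working it through.** **1. The two orders side by side**

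| Endpoint | Protocol 9.4.2 | SAP 3.2 (through 8.6) |
|---|---|---|
| AE/SAE incidence | First | Not in the order (tested in 8.4.1) |
| Ordinal scale, Days 7, 14, 28 | After AE/SAE | First |
| NEWS2 | Day 5, and discharge | Second; Day 7, or discharge if earlier |
| Cytokines, Day 5 | Before respiratory failure | Fifth, after respiratory failure and ICU admission |
| Respiratory failure | After cytokines | Third |
| ICU admission | After respiratory failure | Fourth |
| ICU-free days | In the order | Named in the 3.2.4 title, no hypothesis given |
| ICU length of stay | In the order | Exploratory, outside the hierarchy |
| Hospital length of stay | After ICU | Sixth |
| Hospital-free days | In the order | Absent |
| Oxygen use | Last | Absent |

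**2. Inputs**

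- 100 subjects per arm (protocol 9.1).
- Fisher's exact test, two-sided (protocol 9.4.2).
- Alpha 0.047 (protocol 9.2.3), with 0.049 (SAP 6.1) for comparison.
- The documents give no AE or SAE rate. All rates used in steps 4 to 6 are assumptions, shown as a range.

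**3. Method, checked on the plan's own figure**

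The probability of rejection is

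Pr(reject) = Σₓ Σᵧ Bin(x; 100, p_A) · Bin(y; 100, p_S) · 1{p-value(x, y) ≤ α}.

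For the primary endpoint (8% versus 22%, unpooled z-test, two-sided 0.05) this gives 81.28%, against the stated 81.3%. The plan's figure is reproduced. It is not in dispute and serves here only to check the enumeration.

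**4. First step under equal AE rates (p_A = p_S)**

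| True rate in both arms | 10% or 90% | 20% or 80% | 30% or 70% | 40% or 60% | 50% |
|---|---|---|---|---|---|
| Passes at α = 0.047 | 2.5% | 3.2% | 3.3% | 3.6% | 3.3% |
| Passes at α = 0.049 | 2.9% | 3.2% | 3.5% | 3.6% | 4.0% |

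In one-point steps from 10% to 90%, the range is 2.5% to 3.7% at 0.047 (the maximum is near 42%) and 2.9% to 4.0% at 0.049. At 0.047 the first step therefore fails in 100 − 3.7 = 96.3% to 100 − 2.5 = 97.5% of trials. By symmetry, half of each passing probability is rejection with more events on Ampion.

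**5. First step under modest AE differences, α = 0.047**

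- Ampion 5 points lower: 50% to 45% passes in 8.1%, 30% to 25% in 9.1%, 20% to 15% in 11.0%.
- Ampion 10 points higher: 50% to 60% passes in 24.9%, almost all in the direction of harm.

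A drug with a 10-point excess of events would thus reach the efficacy tests more often than one with a 5-point reduction.

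**6. If the planned benefit carried over to SAEs**

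The planned difference is 22 − 8 = 14 points. If SAE incidence were the first step and fell by that amount, Fisher's test at 0.047 would pass in:

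- 74% at 22% versus 8%,
- 59% at 30% versus 16%,
- 49% at 40% versus 26%.

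**The case against.** The strongest reply is that the SAP already deals with this. Protocol 9.1 leaves the details of the analyses to the SAP, the SAP order has no AE step, and SAP Section 9 lists the hierarchical ordering among the changes. This has weight: the AE step is a defect of the protocol order only. But leaving details to the SAP does not withdraw an order printed in the protocol, and Section 9 neither shows the differences nor says which order governs.

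A second reply is that no stopping rule is written. The sentence introducing the protocol table speaks of efficacy endpoints, and protocol 9.3.1.4 describes safety data as tabulated, so the hierarchy might be meant for efficacy only. That is arguable. However, the safety row is the first row of the table, nothing exempts it, and the protocol's reason for not adjusting alpha holds only with a stop at the first failure.

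A third reply is that an effective drug may lower SAEs, since death is an SAE (protocol 8.2). This stands, and it limits the claim. A reader might infer that an effective Ampion would almost always be barred from secondary claims. The documents do not support that: the 96% to 97% figure assumes equal AE rates, and step 6 shows much higher passing rates if SAEs fall. Nor is equal safety certain to block the later tests. The row also names two incidences, AEs and SAEs, without saying which one decides the step.

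Finally, SAP 8.6 calls the secondaries supportive, and this is a Phase II trial. That lowers the stakes, but both documents chose formal ordered testing, so the order should be unambiguous before unblinding.

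**Conclusion.** The point holds in limited form. As written, the protocol makes a significant AE/SAE difference, in either direction, the condition for formally testing any secondary efficacy endpoint. With truly equal AE rates (assumed, 10% to 90%), 100 per arm and Fisher's test at 0.047, that condition is met in about 2.5% to 3.7% of trials. If SAE incidence were the deciding test and fell by 14 points, it would be met in about 49% to 74%, for assumed control rates of 40% down to 22%. Both results rest on the implied stopping rule and on the protocol order being the one applied.

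The conflict between the two orders needs no assumption and can be read directly from the documents. A reader might also infer that the primary result is at risk. It is not: the primary endpoint is tested separately, before the secondaries. The plan should be corrected before unblinding.

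**What to change.** 1. In protocol 9.4.2, remove AE/SAE incidence from the hierarchy and report it by arm with a risk difference and 95% confidence interval. If the test in SAP 8.4.1 is kept, label it as outside the hierarchy and not alpha-controlled.
2. Print one identical efficacy order in both documents, based on SAP 3.2, and state that testing stops at the first non-significant step. Each step needs a single defined test. At present SAP 3.2.1 combines three timepoints, and 3.2.5 covers cytokines without naming a lead analyte.
3. In SAP Section 9, list every difference from the protocol order and state that the SAP order governs. The list should cover the AE step, the cytokine position, ICU length of stay, ICU-free days, NEWS2 timing, oxygen use and hospital-free days.

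Costs: no alpha-controlled AE test remains. Oxygen use, hospital-free days and ICU length of stay become exploratory unless added at the end of the order. The change to the protocol needs a written amendment approved by the sponsor, the IRB/IEC and the health authorities (protocol 10.3). Sample size and data collection do not change.

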9. CHANGES FROM PROTOCOL-SPECIFIED ANALYSES

The statistical analysis of this study has been modified by this amendment to the SAP: The primary endpoint has been amended to assesses the effect of Ampion compared to placebo on prevention of need for mechanical ventilation or death prior to day 28, instead of mortality alone; and, secondary endpoints have been listed in a hierarchical order.

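### The Day 14 and Day 28 ordinal-scale endpoints and the NEWS2 endpoints are defined and tested differently in protocol and SAP, and the protocol's stop at discharge ignores a later death

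*Protocol*

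**What the plan says.** **Ordinal scale.** Protocol Section 9.4.2 has three items: "Change in ordinal scale from baseline through Day 7"; then "Change in ordinal scale from baseline to hospital discharge or day 14 (whichever occurs first"; then the same with Day 28 in place of Day 14. The synopsis (1.1) and Section 3.3.2 define them the same way. SAP Section 3.2.1 is headed "Change in ordinal scale from baseline through Day 7, Day 14 and Day 28", and its text tests the change at each of those days.

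**NEWS2.** Protocol Section 9.4.2 has "Change in NEWS2 score from baseline through Day 5" and a second endpoint running to hospital discharge. SAP Section 3.2.2 has a single endpoint, "Change in NEWS2 score from baseline through Day 7, or discharge if earlier".

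**Hierarchy.** Protocol Section 9.4.2: "The secondary endpoints will be tested in a hierarchical manner in the order presented, and thus no adjustment to the alpha level is necessary". SAP Section 8.6 says that a hierarchical "testing scheme will be employed in the order specified in Section 3.2".

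**Declared changes.** SAP Section 9 names two changes: the composite primary endpoint in place of mortality alone, and that "secondary endpoints have been listed in a hierarchical order".

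**The concern.** In a fixed-order procedure without alpha adjustment, each endpoint is a gate for those after it. If the two governing documents define an early gate differently, they can disagree about which later endpoints may be tested at all. The ordinal and NEWS2 endpoints lead the efficacy part of both sequences, and SAP Section 6.1 runs the 30-subject interim on secondary as well as primary data, so the definitions matter from that look onward.

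The protocol's version also has a fault of its own. Where the score stops at discharge, a patient who goes home and then dies or deteriorates lastingly before the landmark day keeps the discharge score. On this scale a discharged patient normally scores better than at baseline, so a death can be recorded as an improvement. Protocol Section 5.2 has clinical status recorded to Day 60, so information that the trial collects is left out of the endpoint.

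**Working it through.** **1. The plan's own figure.** No power or sample size is given for these endpoints. The only design figure is the primary endpoint's 81.3% power (8% against 22%, 100 per arm). Enumeration with the unpooled z-test reproduces it (81.28%), but it does not bear on this point.

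**2. Side by side.**

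| Item | Protocol 9.4.2 | SAP 3.2 |
|---|---|---|
| Ordinal, Day 7 | fixed day | fixed day (same) |
| Ordinal, Day 14 | discharge if earlier | fixed day |
| Ordinal, Day 28 | discharge if earlier | fixed day |
| NEWS2 | two: through Day 5; to discharge | one: Day 7 or earlier discharge |
| Test | repeated-measures ANOVA | Wilcoxon rank-sum; ANOVA exploratory |
| Place of AEs/SAEs | first in the order | outside 3.2 (tested in 8.4.1) |
| Place of cytokines | before respiratory failure | after the ICU endpoints |

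The test conflict applies to the Day 7 ordinal endpoint too, although its definition agrees. Under the protocol order, failure on NEWS2 through Day 5 or NEWS2 to discharge stops the sequence before respiratory failure. Neither gate exists in the SAP.

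**3. Effect of stopping at discharge.** Inputs from Protocol Section 5.2: scores 3 to 7 are all in-hospital states, death is 8, and an oxygen-requiring inpatient starts at 4 or more. Let *b* be the baseline score and *d* the score at discharge, for a patient who dies after discharge and before the landmark day.

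- Protocol change: *d* − *b*.
- Fixed-day change with death scored 8: 8 − *b*.
- Difference: (8 − *b*) − (*d* − *b*) = 8 − *d*.

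For *b* = 4, *d* = 2, death on Day 20: the protocol's Day 28 change is 2 − 4 = −2; the fixed-day change is 8 − 4 = +4; the difference is 6. With *d* = 1 the protocol gives −3 and the difference is 7. From *b* = 5 the protocol gives −3 or −4 against +3. In this example the Day 14 score is unaffected: the patient is alive then, and if still at 2, both rules give −2.

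Each such death per 100 patients moves the arm mean by 6/100 = 0.06 to 7/100 = 0.07 points.

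**4. Illustration with assumed inputs.** All of these are assumptions: 100 per arm; baseline 4 or 5 in 70% and 30%; in both arms 8% in-hospital deaths and 5% still ventilated; the rest discharged at 1 or 2; post-discharge deaths among discharged patients of one arm only; Wilcoxon at 5%; 2,000 simulated trials.

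| Post-discharge death rate | Rejects, stopped at discharge | Rejects, fixed day |
|---|---|---|
| 3% | 4.7% | 6.3% |
| 5% | 5.0% | 9.6% |
| 10% | 4.5% | 23.1% |

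The middle column stays near 5% by construction, because that endpoint cannot register these deaths. The table shows the mechanism and does not forecast this trial.

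**5. Rules for death and missing status.** Protocol Section 9.5 covers unknown mortality status; SAP Section 7.1 covers the primary endpoint. Neither says how a death enters the ordinal score, so the +4 above needs the added rule that death is scored 8.

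**6. Schedule.** The ordinal row in Protocol Section 1.2 runs daily to Day 7, then Days 28 and 60. SAP Section 12 adds Days 7 and 14. A fixed Day 28 score therefore already has a protocol visit. A fixed Day 14 score does not.

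**The case against.** The case against is substantial in parts.

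- *Post-discharge deaths are not lost to the trial.* This stands. The primary endpoint counts deaths by Day 28 whether or not the patient has gone home, mortality is recorded at Days 28 and 60, and the SAP's sensitivity analysis addresses discharged patients who cannot be reached.
- *The SAP governs.* A reader might infer that the sponsor is free to pick a definition once results are known. The documents do not support that: Protocol Section 9.1 leaves analysis details to the SAP, and Section 3.4 requires SAP approval before unblinding. Even so, replacing an endpoint is more than a detail of analysis, and the protocol still states the other definition as current.
- *SAP Section 9 is weak evidence.* It describes a move away from mortality alone, which the current protocol no longer uses, so its silence says little about intent. That is fair. It remains true that neither document tells the reader that the definitions and tests differ.
- *Stopping at discharge can be sensible.* For NEWS2 it can. The score needs vital signs and oxygen saturation, and later contacts are mostly by telephone; the SAP's NEWS2 endpoint also stops at discharge. That reasoning does not extend to the ordinal score, which both schedules collect at Days 28 and 60.

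**Conclusion.** The mismatch is in the current text of both documents: two of the three ordinal endpoints, all NEWS2 endpoints, the tests for both, and the testing order. The protocol's stop at discharge is a stated rule that gives a misleading score. For a patient who dies between discharge and the landmark day, it differs by 6 or 7 points from a fixed-day score with death at 8, assuming a discharge score of 2 or 1.

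Several broader readings are not supported:

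- That the whole ordinal family stops at discharge. The Day 7 endpoint does not.
- That every post-discharge death or readmission is misclassified. A patient readmitted on Day 10 and home again by Day 28 can have the same Day 28 score under both rules.
- That the SAP already solves the problem. It removes the stop at discharge but leaves the scoring of deaths unstated.
- That either arm is favoured. The documents give no post-discharge death rate, overall or by arm, so neither the frequency nor the direction of the effect can be stated.

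The consequence is limited to the secondary endpoints and to which of them can be reached in the hierarchy. It should be corrected, but it does not touch the primary analysis.

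**What to change.** Before any unblinded look, including the 30-subject interim:

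1. Amend Protocol 1.1, 3.3.2 and 9.4.2 to the SAP's fixed-day ordinal scores at Days 14 and 28.
2. State in both documents that death by the landmark day is scored 8.
3. Add the Day 14 ordinal assessment already in the SAP schedule to Protocol 1.2 and 5.1.5.
4. Choose one NEWS2 definition and use it in both documents.
5. Name one test per endpoint in both documents; the SAP's Wilcoxon rank-sum test is suitable.
6. Give one hierarchy order in both documents, including where, if anywhere, AEs/SAEs and cytokines stand.
7. List these changes in SAP Section 9.

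Most of this is redrafting. The one operational cost is Day 14: a telephone contact for discharged patients, or a rule for scoring Day 14 from recorded status. Day 28 needs no new visit, and the sample size does not change.

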There are two endpoints in this set. Hypotheses about both will be tested independently. The first hypothesis about the percentage of patients who are admitted to the ICU involves all patients. The second hypothesis involves only patients who are admitted to the ICU. Since it is not known how many many patients will be admitted to the ICU, the testing of the second hypothesis will be considered exploratory and not part of the hierachial testing scheme.

The first hypotheses to be tested is:

$$H_0: \pi_A = \pi_S \text{ versus } H_A: \pi_A \neq \pi_S$$

Where π_A and π_S represent the percentage of patients who are admitted to the ICU for Ampion and Placebo during the first 28 days after randomization. The difference between Ampion and Placebo will be tested via an appropriate chi-square test or Fisher's exact test utilizing PROC FREQ with the EXACT option, if needed.

The second hypothesis to be tested is:

$$H_0: \text{Median}_A = \text{Median}_S \text{ versus } H_A: \text{Median}_A \neq \text{Median}_S$$

Where Median_A and Median_S are the median ICU length of stay for the Ampion and placebo groups. Assuming there is no censoring, this will be tested using the Wilcoxon rank sum test via PROC NPAR1WAY. If censoring occurs, e.g., death, then the log rank test will be used based on PROC LIFETEST.

3.2.5 Modulation of cytokine levels from baseline to Day 5.

The hypotheses to be tested are:

$$H_0: \mu_A = \mu_S \text{ versus } H_A: \mu_A \neq \mu_S$$

Where μ_A and μ_S represent the mean percent change from baseline in the cytokine levels at day 5 for Ampion and Placebo after randomization. The difference between Ampion and Placebo with respect to the percent change from baseline at day 5 will be tested utilizing a two sample t-test via PROC TTEST. To assess any potential time trends an exploratory repeated measures analysis of variance will be performed with terms for treatment, time and the interaction of the two. This will be done utilizing PROC GLM with the REPEATED option.

Statistical Analysis Plan (SAP) for Clinical Study AP-017

3.2.6 Hospital length of stay.

The hypotheses to be tested are:

$$H_0: \text{Median}_A = \text{Median}_S \text{ versus } H_A: \text{Median}_A \neq \text{Median}_S$$

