Where Median_A and Median_S are the median hospital length of stay for the Ampion and placebo groups. Assuming there is no censoring, this will be tested using the Wilcoxon rank sum test via PROC NPAR1WAY. If censoring occurs, e.g., death, then the log rank test will be used based on PROC LIFETEST.

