10.2 Efficacy (Analysis population: ITT)

10.2.1	Summary of Mechanical Ventilation or Mortality
10.2.2	Summary of Change in Ordinal Scale
10.2.3	Summary of Change in NEWS2 Score
10.2.4	Summary of Progression to Respiratory Failure over Time to Day 28
10.2.5	Summary of ICU admission
10.2.6	Summary of ICU LOS
10.2.7	Summary of Change in Cytokine Levels from baseline to Day 5
10.2.8	Summary of Hospital LOS

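### Length of stay (hospital and ICU) has one test in the protocol and two others in the SAP, with no common rule for in-hospital death; hospital-free days appears in one list only, and SAP section 9 declares none of this

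*Protocol*

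**What the plan says.** **Protocol.** Section 9.4.2 lists the secondary endpoints as a fixed testing sequence. Under hospital stay it has two entries: "Hospital length of stay (LOS) from admission to discharge" and "Hospital-free days through Day 28". The synopsis (1.1) and section 3.3.2 list only the first. For the test, 9.4.2 states: "The length of stay endpoints are also single incident endpoints the differences between the treatment groups will be tested using two sample t-test". The plural covers ICU length of stay, which is in the same table. Section 5.2 computes hospital stay from the admission and discharge dates. It gives no rule for a patient who dies before discharge.

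**SAP.** The last secondary endpoint is "3.2.6 Hospital length of stay", with a hypothesis on medians. The test is conditional: "Assuming there is no censoring, this will be tested using the Wilcoxon rank sum test via PROC NPAR1WAY", followed by "If censoring occurs, e.g., death, then the log rank test will be used based on PROC LIFETEST". Section 3.2.4 uses the same wording for ICU length of stay and makes that test exploratory, outside the hierarchy. The planned table is "Summary of Hospital LOS". Hospital-free days is in no endpoint, table, listing or figure of the SAP.

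**Declared changes.** SAP section 9 mentions the amended primary endpoint and that "secondary endpoints have been listed in a hierarchical order". It mentions neither the length-of-stay tests nor hospital-free days.

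**The concern.** A step in a fixed sequence needs one endpoint and one test. Here two approved documents name different tests for the same step, on different parameters (means against medians). One document also carries an extra step that the other lacks.

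The difference is more than a matter of skewness, because the tests treat in-hospital death differently:

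- **t-test or Wilcoxon on dates.** If death closes the stay, an early death counts as a short stay, which is the favourable direction. If there is no discharge date, the patient drops out of a comparison that should include all randomised patients.
- **Log-rank with death censored.** This compares discharge rates among patients still in hospital. Reading it as a comparison of median stay, as the SAP does, assumes that those who died would have been discharged at the same rate as those who remained.

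Neither document says which behaviour is intended. At stake is whether this step is declared significant, and whether a reader can tell which analysis was planned.

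**Working it through.** **1. The plan's own figure.** The only power figure is for the primary endpoint: 8% against 22%, 100 per arm, two-sided 5%, unpooled z-test, 81.3%. Summing P(x)P(y) over all 101 × 101 binomial outcomes with |p1 − p2| / √[p1(1 − p1)/100 + p2(1 − p2)/100] > 1.96 gives 81.28%. It reproduces. Neither document gives a power, mean, SD or death rate for length of stay.

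**2. Side by side.**

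| | Protocol 9.4.2 | SAP 3.2.4 / 3.2.6 |
|---|---|---|
| Hospital stay endpoints | LOS and hospital-free days | LOS only |
| Parameter | means (implied by the t-test) | medians |
| Test, hospital LOS | t-test | Wilcoxon, or log-rank if censoring |
| Test, ICU LOS | t-test, in the hierarchy | Wilcoxon, or log-rank if censoring; exploratory |
| In-hospital death | no rule | censored, once log-rank applies |
| Listed in SAP section 9 | n/a | no |

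**3. Which SAP branch applies?** P(no death among 200) = (1 − d)^200, where d is an assumed overall death rate (the planning rates of 22% and 8% are for ventilation or death combined):

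- d = 4%: 0.96^200 = 0.0003 (0.03%)
- d = 2%: 0.98^200 = 0.018 (1.8%)
- d = 1%: 0.99^200 = 0.13 (13%)

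So the hospital LOS test is almost always log-rank. The Wilcoxon branch has a real chance only at very low mortality.

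**4. Does the choice of test change the answer?** All inputs here are assumed. There are 100 patients per arm, log-normal stay with a control median of 10 days, deaths uniform over days 1–28, two-sided 0.05 and 1,500 simulated trials (standard error at most √(0.25/1500) = 1.3 points). Death ends the stay for the t-test and Wilcoxon and is censored for log-rank.

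| Setting (deaths Ampion / control) | t-test | Wilcoxon | Log-rank | t-test and log-rank disagree |
|---|---|---|---|---|
| log-SD 0.8, median 20% shorter, no deaths | 39% | 47% | 42% | 5% |
| same, deaths 10% / 10% | 34% | 42% | 32% | 11% |
| same, deaths 5% / 15% | 42% | 53% | 69% | 27% |
| log-SD 1.0, median 25% shorter, deaths 5% / 15% | 33% | 53% | 67% | 34% |

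A second set of assumptions (median 8 days, log-SD 0.7, stay 20% shorter, 800 trials) behaves the same way. With deaths 4% on Ampion and 11% on control, power is 55%, 61% and 69% for t-test, Wilcoxon and log-rank, and t-test and log-rank disagree in 16% of trials. With 8% deaths in each arm it is 45%, 52% and 38%.

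The ranking depends on whether deaths differ between arms. Log-rank leads when they do and is the weakest of the three when they are equal.

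**The case against.** **The SAP governs.** Protocol 9.1 leaves analysis details to the SAP, and Protocol 3.4 requires SAP approval before unblinding. A reader might infer that the team could pick a test after seeing the results. The documents do not support that: the SAP states a rule, and step 3 shows that it almost always selects log-rank. What stands against the plan is narrower. Replacing a named test is a change rather than a detail, and SAP section 9 exists to record such changes.

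**Hospital-free days.** A reader might infer that a better endpoint was quietly removed. The documents do not support that either. It is in one of three protocol lists, so the SAP agrees with the other two, and a stray line in 9.4.2 is the simpler explanation. Nothing defines it or scores death as zero. Nor is it stated that the t-test sentence covers it.

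**It should replace length of stay.** With death scored as zero it gains power only when deaths differ. With 8% deaths in each arm it has 46%, against 52% for Wilcoxon on stay. That does not justify swapping endpoints.

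**Low in the hierarchy.** This is true. Hospital stay is the last SAP secondary and the second-to-last protocol objective, so earlier steps must succeed before it is formally tested. The disagreement percentages ignore that gate, so the practical consequence is smaller than they suggest.

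**Wilcoxon or log-rank suits skewed stays better than a t-test.** That is arguable, and it supports keeping a rank-based test. It does not settle how deaths are handled.

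**Conclusion.** The point holds as a reconciliation and declaration defect with a real statistical component. The two documents conflict on the test for hospital and ICU length of stay. The protocol's endpoint lists conflict on hospital-free days. SAP section 9 is silent on both. No stated rule deals adequately with in-hospital death.

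The text comparison needs no assumptions. The sizes do: disagreement of roughly 5% to 34% between t-test and log-rank rests on assumed stay distributions, treatment effects, death rates and death timing. It applies only if testing reaches this step. The dominance of the log-rank branch rests on an assumed death rate of about 1% or more. The point should be corrected before unblinding. It does not touch the primary endpoint.

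**What to change.** 1. Keep hospital length of stay, the endpoint in every list, as the hierarchical step.
2. In Protocol 9.4.2 and SAP 3.2.6, name one test and one death rule that does not treat death as an early discharge. One example is a Wilcoxon rank-sum test in all ITT patients with in-hospital death given the worst rank. State also how a stay still open at the last follow-up is ranked.
3. Replace the protocol's t-test sentence for both hospital and ICU length of stay, so that ICU stay is not left without a test. Say in both documents whether ICU stay is exploratory.
4. Remove the data-dependent Wilcoxon/log-rank switch from SAP 3.2.4 and 3.2.6.
5. Either delete hospital-free days from 9.4.2 or define it (death = 0) as a supportive analysis outside the hierarchy.
6. List these changes in SAP section 9.

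**Cost.** No new data are needed, because admission, discharge and mortality are already collected (Protocol 5.2). The protocol edits need an amendment with the approvals in Protocol 10.3. A worst-rank test mixes survival with stay, so length of stay among survivors should also be reported descriptively.
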